After the subject-specific FHO is ready, the stroke participant and his/her paired PT will be called to participate the 1st and 2nd lab-based training with ReIn-hand device. During these 2 visits, the assigned PT (1st test) or the research PT (2nd test) will train the stroke participant to use his/her FHO and the ReIn-Hand software on a mobile phone, until the stroke participant demonstrates the ability in using the device independently twice in a row. On the 2nd test, the research PT will also re-test partial of the clinical assessments, however, this time with the assistance of ReIn-Hand device. Each of these 2 visits is expected to last about 3 hours. During these 2 visits, we will measure the time for a stroke participant to learn the use of ReIn-Hand device. Within 0-3 days after the 1st (for PTs) or the 2nd lab-based training (for individuals with stroke), a 5min user survey to report the level of ease-of-use of the ReIn-Hand device will be conducted.

[figure not shown]

Figure 4. EEG Experimental setup showing a subject using the ACT^{3D} robot while high-density EEG and surface EMG signals will be simultaneously recorded. Visual feedback will be displayed on a computer screen.

F.2. Home-based practice

After the 3 lab-based visits as listed above, 4 out of 20 stroke participants will further participate the home-based practice. They will take the ReIn-Hand device, including his/her FHO, the mobile phone with ReIn-Hand software, and the electronic stimulator (300 PV, Empi, Minnesota, USA, a FDA approved clinical device) back to home. At home, they will perform 20 trials of pre-set tasks, like reaching and grasping, per session (1 hour), 1 session per day, 7 days per week for 12 weeks. During these 12 weeks, they will visit the lab once per week to make necessary device changes, update the partial of the clinical assessments, all without ReIn-hand. These clinical tests will also be re-measured at 1 and 3-month after the home-based practice, again without ReIn-hand.

Both electrodes and electrical stimulator are commercially available devices (300 PV Complete Electrotherapy System, Empi, Inc., St. Paul, MN). Each subject will be assigned task-specific, functional exercises targeted to their individual abilities, deficits, and personal preferences. Stimulation will be provided with the following characteristics:

Amplitude – at motor threshold with the maximum intensity lower than 100 mA
 Frequency – $50\pm20\%$ Hz
 Pulse Duration – 300-400 microseconds
 Ramp/Fall Times and Duty Cycle – adjusted to the task

F.3. Data collection and procession

Main data collection is listed in table 2.

Day 1	#1, Demographic data, #2, Clinical assessments as listed above, #3, Time for a) determining the stimulation /recording electrode positions, b) for scanning,
Day 2	#1, EEG data, #2, EMG data, #3, finger position during hand-opening and graping force data during closing
Day 3	#1, Time for the stroke subject to a) to attach the FHO, b) use the software, including connecting all the cables following the instructions, c) set up the detection rule, and d) clean up. #2, The accuracy in detecting grasping and releasing; and #3, EMG data while performing task, sampled at 1K Hz.
Day 4	Measures #1-3 on Day 2, #4, ARAT and BBT with the assistance of ReIn-Hand.
Home-based test	Measures #1-4 on Day 3 and MAL-14, NSA, and hand opening and closing ability weekly during the 12-week home-based practice, then again at 1 and 3-month after. To the end of the 12-week home-based practice, we will use a GLOC scale (one question survey) to collect user overall satisfiaory level of the ReIn-Hand supported home practice.

Data analysis for evaluating the engineering aspects is listed on Table 3.

Primary measures	Measured by	Expectation
Time for learn-to-use the device	#1 on Day 3 and Day 4	<3 hours in each of the 2 days, and no difference between 2 days ¹ .
Time for setup and cleanup	#1 a) and d) on Days 3 & 4, and during the home-based test	<5 min for each, and significantly less than the

		measure #3 (a) on Day 1
Successful rate on controlling grasping and releasing during reaching	#2 on Days 3, 4, and during the home-based test	a false 'transfer' < 10%
Time delay caused by the device	We will detect the onset of EMG at the extensor measured on days 3 &4, and the onset of stimulation artifact. The latency between them will be calculated.	<350 ms
Difference in Clinical assessments with and without ReIn-Hand	Difference between measure #4 on Day 4 & measure #2 on Day 1	ARAT and BBT with ReIn-Hand will outperform that without ReIn-Hand.
Willingness to use ReIn-Hand at home	#1-3 during the home-based test	Continuous use on daily base.
Cortical activity related to hand open with and without lifting	We will use EEG data to estimate the cortical activity related to the 2 motor tasks pre- and post-home-practice	Post-intervention cortical activity related to these 2 motor tasks become 'closer to' that in healthy control subjects.

¹Ease-of-use feature of the device will be reflected by the <3 hours learning time. We will further study effects of 1) PT's experience with ReIn-Hand, and 2) the number of experimental sessions on the time to learn to use the device. For PT's experience, since [name] already has 4-year experience in using current ReIn-Hand device in stroke participants, we will compare 1) the learning time on day 2 of the group 1 (N=10) working with the 10 PTs versus the time of the group 2 (N=10) working with [name]; and 2) the learning time of group 1 on day 2 with the 10 PTs versus the time of the same group on day 3 with [name]. A non-significant difference for both comparison will suggest non-significance for PT's experience in using the device. For the number of sessions needed to learn to use the device, we will compare the learning time of both groups on day 2 versus that on day 3. A non-significant difference will suggest sufficiency of one session in learning the device.

Evaluation of the usability of the ReIn-Hand: Within 0-3 days after Day 3, the 10 PTs and the 20 stroke participants will finish a 5min user survey to report the level of ease-of-use of the ReIn-Hand device. Items that will be rated (on ordinal scale 0-5, with the easiest use at 5) include: 1) determination of the stimulation/recording electrode positions (PT only), 2) setting up the initial detection rule (PT only), 3) fine adjustment of the detection rule (both), 4) placement of the FHO (both), 5) using the mobile phone software (both), 6) performance of the trained functional task (both). We expect to observe users' grades $\geq 4/5$, with grades $\leq 3/5$ will be queried for explanation and compiled for future design modifications.

Transportation: Participants will be given reimbursement for transportation expenses. Participants are encouraged to take public transportation, or to drive and park in Northwestern Medical School parking lots (located at [name] or [name]) where a parking sticker

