We plan to recruit about 100 moderately to severely impaired stroke subjects who have some shoulder and elbow control, but lack hand function (UE FMA Scores of 10-40/66, CMcM \leq 4) to participate in the cross-sessional experiments. Individuals with stroke will be selected from the Clinical Research Registry (CRR) housed at the ShirleyRyan AbilityLab which contains more than 700 members, as well as from stroke survivors residing in the Chicagoland area who wish to participate in the study. Recruitment of subjects who are currently enrolled in the Clinical Research Registry will be done via phone call and email. Recruitment of stroke survivors residing in the Chicagoland will be done via flyer or on-clinical-site survey for willingness of participation. In addition, in order to facilitate recruitment, we will post this study on The New Normal (TNN¹) Match matchmaking portal, a National Institutes of Health (NIH) funded collaborative project to give communities access to information about healthy research opportunities. These stroke subjects will go through 1 or 2 stages (i.e., the 1st stage as remote prescreening which is optional and the 2nd one as on-site screening for eligibility test which is required) of eligibility tests. Recruitment for stroke participants will be ended when 20 individuals with moderate to severe impairment post-stroke are enrolled and finished the data collection.

Once confirmed their desire and willingness to participate, the potential participant will be asked to sign an online e-Consent form, or a hard copy consent form. For individuals who signed the e-Consent form and passed the remote pre-screen, a hard copy of consent form will still be signed on the first on-campus visit.

We will recruit 10 healthy individuals at least 45 years old. These individuals will participate in one session of the EEG experiment, and will provide control data to compare against the stroke individuals who partake in the home-based practice.

¹ <https://www.nucats.northwestern.edu/news/2020/northwestern-new-normal-launch.html>.

Also, 10 independent physical therapists (PTs) or senior physical therapy students (SPTs), who have experience working with stroke subjects and using FES, will be recruited for setting up the ReIn-Hand device for stroke users, and then teaching stroke users to use the device. Stroke, PT and SPT users will provide feedback from clinicians and stroke users' angles, respectively.

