After the eConsent or Consent form is obtained either online or as a hard copy, a qualified team member will call the stroke participant to conduct a phone survey to screen their current medical status and history and willingness to participate in the study. If a stroke participant agrees to have a remote section using video call, like zoom, FaceTime, WhatsApp etc., a video call will be scheduled to assess three short-version clinical assessments (MOCA, FMA and Chedoke). These remote sections will allow the team members to pre-screen the eligibility of a stroke participant without requiring an in-person visit. These two remote sessions (phone survey and video call) may be combined, with a total of about 30 minutes.

E.1. Inclusion and Exclusion criteria

Stroke participants should have sustained a unilateral lesion at least 6 weeks prior to participation in this project. The following inclusion criteria will be applied to the participants: 1) Paresis confined to one side, with substantial motor impairment of the upper limb; 2) Absence of motor impairment in the unimpaired limb; 3) Absence of a brainstem and/or cerebellar lesion; 4) Absence of severe concurrent medical problems (e.g. cardiorespiratory impairment, changes in management of hypertension); 5) Absence of any acute or chronic painful condition in the upper extremities or spine; 6) Absence of cardiac pacemaker; 7) seizure free; 8) no Botox within the last 6 months; 9) Capacity to provide informed consent; 10) Ability to elevate their limb against gravity up to horizontal and to generate some active elbow extension; 11) Ability to achieve functional grasp and release with the assistance of an ES device with the help of an experienced professional physical therapist; and 12) Not in pregnant or planning to become pregnant. Overpressure at the end of the range of motion will be used as a medical screening measure to verify the absence of inflammatory condition at the shoulder, elbow, wrist, and fingers. The shoulder passive range of motion of the affected upper extremity will be measured using a goniometer based on adapted methods. Maximum grip and key pinch forces for each participant will also be measured using a hand dynamometer and a pinch gauge. The impairment level of the upper extremity and the wrist/hand will be evaluated by a research physical therapist using Fugl-Meyer score.

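### The under-3-hour part of the learning-time criterion has little room to fail and is open to completer selection, because no rule counts people who do not learn or who leave during training

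*Protocol*

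**What the plan says.** - **Recruitment stop (protocol, E. Selection of Subjects).** "Recruitment for stroke participants will be ended when 20 individuals with moderate to severe impairment post-stroke are enrolled and finished the data collection". The number who may start training is left open.
- **End of the learning clock (F.1.2).** Training at each of two visits goes on "until the stroke participant demonstrates the ability in using the device independently twice in a row". No maximum time is given.
- **Length of the visits (F.1.2).** "Each of these 2 visits is expected to last about 3 hours". The second visit also holds other work: "On the 2nd test, the research PT will also re-test partial of the clinical assessments".
- **Criterion (F.3, Table 3).** The expectation for learning time is "<3 hours in each of the 2 days, and no difference between 2 days". Footnote 1 makes the under-3-hour time the indicator of ease of use.
- **Groups compared (footnote 1).** Group 1 (10 participants, trained by the clinical therapists) is compared with group 2 (10 participants, trained by the research therapist).
- **SAP.** Its t-tests on therapist experience and session number are assigned to participant satisfaction. Learning time does not appear.

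The plan does not define an analysis set for learning time. It does not say whether the 3 hours applies to each person or to a mean, and it does not say how to record someone who has not learned by the end of the visit or who withdraws during training.

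One labelling point needs reconciling. Table 3 takes learning time from Days 3 and 4, its footnote speaks of days 2 and 3, and Table 2 makes Day 2 the EEG day. I read all of these as the two training visits.

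**The concern.** Two features push the under-3-hour result the same way. First, the pass mark coincides with the planned observation window, so a visit that keeps to schedule produces a passing time or no time. Second, recruitment replaces anyone who leaves before finishing, and the planned comparison groups have room for exactly the 20 finishers. Failing to master the device is a plausible reason to leave, so missing learning times may be related to the outcome.

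At stake is the conclusion that the device is easy to learn, which supports the protocol's case for home use under Objective 1. A figure based on those who learned and stayed would overstate how many eligible patients can learn it.

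**Working it through.** The plan gives no required success share, drop-out rate or sample-size calculation for learning time, so it has no figure to reproduce. The checks below use its stated quantities and labelled assumptions.

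**1. Threshold against window.** Threshold 3 h (Table 3); expected visit about 3 h (F.1.2); ratio 3/3 = 1.0. In the second visit the re-tests take part of that time, so less than 3 h is left for training.

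**2. What a mean of recorded times would show.** Assume, for illustration only, that visits stop at 3 h, that only completed times are averaged, and that true times are lognormal with median m and log-scale SD 0.5. Let z = ln(3/m)/0.5. The share above 3 h is 1 − Φ(z). The true mean is m·exp(0.125). The mean of recorded times is m·exp(0.125)·Φ(z − 0.5)/Φ(z).

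| m (h) | Share above 3 h | True mean (h) | Mean of recorded times (h) |
|---|---|---|---|
| 1.5 | 8% | 1.70 | 1.51 |
| 2.5 | 36% | 2.83 | 1.97 |
| 3 | 50% | 3.40 | 2.10 |
| 4 | 72% | 4.53 | 2.26 |

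The last column stays below 3 h by construction, even when most people need longer.

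**3. Who is counted.** Groups: 10 + 10 = 20, equal to the number of finishers at which recruitment stops. If every non-learner left and was replaced, the expected number of starters needed is 20/p, where p is the true share who learn. That gives 22.2, 25 and 28.6 starters for p = 90%, 80% and 70%. The finishers would show 20/20 in each case.

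**4. Worst-case size.** Let k people start training, do not finish and do not meet the criterion (k is assumed; the plan gives no figure). The share is 20/(20 + k), with exact (Clopper-Pearson) 95% limits.

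| k | Share meeting <3 h | Exact 95% CI |
|---|---|---|
| 0 | 20/20 = 100% | 83% to 100% |
| 2 | 20/22 = 91% | 71% to 99% |
| 5 | 20/25 = 80% | 59% to 93% |
| 10 | 20/30 = 67% | 47% to 83% |

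**5. What the preliminary data exclude.** Section D (Objective 1) reports that all 8 participants learned the laptop version within one 3-hour session. The exact lower 95% limit for 8/8 is 0.025^(1/8) = 0.63, so a true failure share of up to about 37% is not excluded.

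**6. The other half of the criterion.** For no difference between the two days, a paired t-test on 20 people (two-sided 5% level assumed) has 80% power at a standardised difference of 0.66 and 92% at 0.8.

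**The case against.** The strongest reply is that the plan never restricts the analysis to finishers. Section E gives a recruitment stop, and 10 + 10 are planned group sizes. This stands: a reader might take a completers-only set as stated, but it is an inference from section E and footnote 1 of Table 3. It is the natural reading, and nothing in either document points to another set.

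A reader might also infer that the criterion cannot fail. The documents do not support that. Three hours is an expected length, training continues until success, and a time of 3.5 h could be recorded and would miss the expectation. The no-difference part of the same row can fail too (step 6). The point is therefore confined to the under-3-hour part.

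Not finishing is also not the same as not learning. A slow learner can complete data collection and be among the 20. Someone who leaves later, for example one of the 4 who go on to home practice, may already have a valid short time. So step 4 is a worst case, not an estimate.

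Finally, section E says "We plan to recruit about 100 moderately to severely impaired stroke subjects", and it would be wrong to read 100 against 20 as loss during training. Those 100 have still to pass eligibility testing. The entry criterion "Ability to achieve functional grasp and release with the assistance of an ES device" and the 8-of-8 result both suggest that failures may be few. Neither replaces a rule for recording them.

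**Conclusion.** The concern holds in limited form. The under-3-hour part of the learning-time criterion has little room to fail and is open to completer selection. Four things combine: the threshold equals the expected visit length, recruitment runs until 20 people have finished, the learning-time groups sum to 20, and no rule counts a person who does not learn or who leaves during training.

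The direction of any bias is toward success. Its size cannot be fixed from the documents. The 91%, 80% and 67% figures assume 2, 5 or 10 non-finishers, all of them learning failures. If nobody leaves during training and over-running times are recorded, there is no bias. The conclusion also rests on the inference that the 20 analysed are the 20 who finish.

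This should be changed before analysis, because a primary measure depends on it and the remedy is cheap.

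**What to change.** In the SAP, and in footnote 1 of Table 3:

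1. Define the learning-time analysis set as everyone who starts the first training visit.
2. State a maximum observation time for training, counted without the time spent on re-tests and no shorter than the 3-hour threshold.
3. Count as not meeting <3 h anyone who has not reached the twice-in-a-row criterion by that time, and anyone who withdraws during training before reaching it.
4. Keep the observed time of anyone who reached the criterion and left later.
5. Report the proportion meeting <3 h with an exact 95% CI, and list the reasons for withdrawal.
6. Add a sensitivity analysis that excludes withdrawals clearly unrelated to the device, since counting all of them as failures may be too harsh.
7. If times are also summarised, censor withdrawals at the time they left, not at the end of the visit. Say that leaving because of difficulty learning makes such censoring informative. The conclusion should rest on the proportion.
8. Reconcile the day labels in Tables 2 and 3 and the footnote.

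Recruitment to 20 finishers can stay, and no procedure changes. The cost is some SAP wording, one extra data field (criterion reached or not, with the time of leaving and the reason), and a success figure that may be less favourable.

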The device will translate the use of ReIn-Hand device outside the laboratory/clinic: Home-based practice can be beneficial to our targeted population^{90,91}. Due to the large variation in movement ability following stroke, the configuration of recording/stimulation electrodes requires it to be subject-specific. We therefore propose to perform a 3D scan of the subject's forearm/hand followed by a 3D-printing of a subject-specific orthosis with recording and stimulation electrodes embedded to fit individual user's needs. Together with the ReIn-Hand detecting platform on a smart phone, the proposed device will be portable, individualized, easy-to-use, and low-cost, thus having potential for widespread home-based practice.

D. Specific Objectives

The realization of this novel EMG-driven FES device that can be used both in the clinic and at home will be through the following specific aims:

Objectives 1: Develop a real-time ReIn-Hand opening platform as a portable device for home use
We will design a proof of concept FES device that is portable and user-friendly, incorporates graphical user-interfaces, and provides Reliable and Intuitive hand (ReIn-Hand) opening during functional use of the shoulder/elbow. The control algorithms of ReIn-Hand have already been developed on a laptop system for 4 different functional hand tasks. Preliminary results in 8 participants with moderate to severe chronic hand paresis are promising. All subjects learned to use this platform within one 3-hour session, which demonstrates the efficacy of our current algorithms and the intuitiveness of our current control. After a 7-week laboratory-based intervention using the ReIn-Hand, all subjects demonstrated improvements in sensory/motor assessments, and showed changes in related cortical activities and integrity of white matter (see preliminary results). These results provide mechanistic evidence of the efficacy of the current system, and suggest that it is worthy to improve the ease-of-use utilities of ReIn-Hand system to make it suitable for a home-based intervention. The necessity of this aim is therefore to transfer the current algorithms to a portable device (i.e., smart phone), to enable automatic parameter adjustment based on user feedback, and to make this platform sufficiently user-friendly, such that ReIn-Hand assisted functional intervention can be safely and easily implemented both in the clinic and at home.

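### Earlier ReIn-Hand users are neither excluded nor recorded, so the learning-time, accuracy and ease-of-use results may not be those of new users

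*Protocol*

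**What the plan says.** **Eligibility.** Protocol section E.1 introduces its list with "The following inclusion criteria will be applied to the participants: 1) Paresis confined to one side, with substantial motor impairment of the upper limb" and continues to item 12. The only item about an earlier treatment is "8) no Botox within the last 6 months". Section E adds the UE FMA range of 10-40 and the CMcM limit of 4. The phone survey, described just before E.1, is meant "to screen their current medical status and history and willingness to participate in the study"; it does not name device exposure. The exclusion for people with ties to the investigators stands in the E.1 paragraph on physical therapists (PTs) and PT students, and does not cover stroke participants.

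**Earlier users.** Section D, Objective 1, reports: "Preliminary results in 8 participants with moderate to severe chronic hand paresis are promising". It adds that "All subjects learned to use this platform within one 3-hour session", and then: "After a 7-week laboratory-based intervention using the ReIn-Hand, all subjects demonstrated improvements in sensory/motor assessments". That work ran on a laptop system. Footnote 1 to Table 3 says that the research PT "already has 4-year experience in using current ReIn-Hand device in stroke participants".

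**Outcomes.** The first primary measure in Table 3 is learning time, with the expectation "<3 hours in each of the 2 days, and no difference between 2 days". The footnote treats learning time under 3 hours as the evidence of ease of use. It also takes a non-significant difference between sessions to mean that one session is enough. Table 3 further sets a false-transfer rate below 10%, and a user survey rates ease of use.

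**Recording and analysis.** Table 2 lists demographic data and clinical assessments for Day 1, with no item for earlier device use. The SAP has no term, subgroup or exclusion for it.

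**The concern.** A claim that a device is quick to learn is a claim about people who have not used it. E.1 as written admits people who have been trained on an earlier version, and nothing in the data collection would identify them afterwards.

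For the outcomes concerned, the distortion would run mostly in the hoped-for direction:

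- **Learning time.** An earlier user would be expected to need less of it.
- **Session-to-session change.** Someone with little left to learn should differ little between the two lab sessions. This pulls the comparison towards the non-significant result that the footnote counts as success.
- **Detection accuracy and ease-of-use ratings.** Practice in expressing the intention to open the hand should reduce false transfers and may raise ratings.
- **PT-experience comparison.** With 10 participants per group, an uneven share of earlier users could create or hide a difference. The direction here is not predictable.

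**Working it through.** The documents give no learning times by experience and no count of returning pilot participants, so there is no plan figure to reproduce. The check has a textual part and an illustration.

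**1. Textual check.** The 12 items in E.1 cover lesion and impairment, comorbidity, pain, pacemaker, seizures, Botox, consent, limb ability, response to stimulation and pregnancy. None covers earlier ReIn-Hand use. The same holds for the FMA/CMcM limits, the description of the phone survey, Table 2 and the SAP.

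**2. How many might enrol?** Inputs: 8 known earlier users (Objective 1), a registry of more than 700 (section E), at least 50% of members appropriate (E.1), and 20 completers (section E). Assume that all 8 are registered and still eligible, and that enrolment is unrelated to earlier participation.

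- Pool = 700 × 0.5 = 350.
- Expected number among 20 = 8 × 20 / 350 = 0.46.
- Hypergeometric (350, 8, 20): P(at least 1) = 38%; P(at least 2) = 7%; P(at least 4) = 0.05%.

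This is neither a floor nor a ceiling. Some of the 8 may not be registered or may no longer qualify. On the other hand, past participants may be more willing to volunteer.

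**3. Effect on mean learning time.** Let k of the 20 be earlier users who need a fraction f of a new user's time. Then sample mean = new-user mean × [1 − (k/20)(1 − f)]. Both k and f are assumptions.

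| k | f = 0.25 | f = 0.50 | f = 0.75 |
|---|---|---|---|
| 0 | 0% | 0% | 0% |
| 1 | −3.75% | −2.5% | −1.25% |
| 2 | −7.5% | −5% | −2.5% |
| 4 | −15% | −10% | −5% |
| 8 (all return) | −30% | −20% | −10% |

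**4. Effect on the session comparison.** If earlier users show no change between the two sessions (an assumption), the mean change shrinks by k/20: 5% for k = 1 and 10% for k = 2.

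**5. Effect on the 10 v 10 PT comparison.** Under a random split, k = 2 puts both earlier users in the same group with probability 2 × 0.237 = 47%. For k = 4, a 3:1 split has probability 49.5% and a 4:0 split 8.7%. No SD is given, so these probabilities cannot be turned into a statement about the test.

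**6. After the fix.** k = 0 and the distortion is 0 in every row.

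**The case against.** The strongest reply is that this guards against an event nobody has documented. No passage says that a pilot participant is registered, will be approached or will enrol. That stands: the distortion may be zero, and step 2 puts the expected number below one under its assumptions. The research PT's 4 years of experience gives no participant count and is compatible with the same 8 people.

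Carry-over may also be weak. The pilot ran on a laptop, whereas the phone software and the printed orthosis are new. Table 3 takes learning time from attaching the orthosis, using the software, setting the detection rule and cleaning up. This stands in part. Carry-over to the orthosis and phone steps should be limited, but it is plausible for the detection rule and for control of opening. In addition, F.1.2 continues training until the participant uses the device independently twice in a row, so skill with the device can still shorten the time.

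Three stronger readings are tempting, and the documents do not support them:

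- **The 3-hour criterion would be met only because of earlier users.** All 8 pilot participants learned within one 3-hour session, so nothing in the documents suggests that new users average more than 3 hours.
- **The functional result would be inflated.** ARAT and BBT are compared within person, Day 4 with the device against Day 1 without it. A Day 1 score raised by earlier training would not inflate that difference and could shrink it.
- **The PT comparison would be systematically biased.** Participants are assigned to PTs at random, so any imbalance is due to chance.

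Nor can it be said that all 8 would qualify. All improved, and whether they still meet the FMA and CMcM limits is not stated.

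**Conclusion.** The gap is real: earlier ReIn-Hand users are neither excluded nor identifiable, in a study whose first primary measure is the time to learn the device. If any enrol, learning time, session-to-session change, accuracy and ease-of-use ratings would cease to be those of new users and would tend to favour the device.

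The number of such users and the size of the carry-over are unknown, and either may be zero. With 1 or 2 earlier users, mean learning time would fall by 1.25% to 7.5% over the assumed range of f. The larger entries in the table need several or all of the pilot group to return. This is a cheap improvement to the design. It does not show that the planned results are biased.

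**What to change.** Add one line to E.1: no previous use of any version of ReIn-Hand. Ask about it in the phone survey that already takes history.

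If earlier users are to be kept, record previous use on Day 1. State in the SAP that the learning-time (including session comparison), accuracy, ease-of-use and PT-experience analyses are based on device-naive participants. With k earlier users, those analyses would then have 20 − k participants unless recruitment continues until 20 are device-naive.

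The cost of the first option is one eligibility line, one question and the loss of a small pool of known candidates: 8 documented, against a registry of more than 700.
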